**4.3 Visit 1: Training Day**

1. Urine pregnancy test (if not within 7 days of Visit 0)
2. Volunteers will be trained on the cycle ergometer to reach an exercise level producing a minute ventilation of 20 L/min/m^2 body surface area (BSA). Subjects will be monitored with a standard 3-lead EKG during exercise (15 minutes).
3. MCC
4. Sputum induction

**4.4 Visit 2: Retention Scan (24 hours after Visit 1)**

1. MCC retention scan (30 minutes)

**4.5 Visits 3 (Period 1) and 7 (Period 2): WSP exposure (within 6 weeks of Visit 0 for Period 1 and Visit 5 for Period 2)**

1. Vital signs, oxygen saturation
2. Symptom questionnaire
3. Physical Exam
4. Urine Pregnancy Test (if not previously performed within 7 days)
5. Venipuncture (CBC with differential, serum cytokines, CRP)
6. EBC
7. Spirometry
8. 500 µg/m^3 WSP chamber exposure for 2 hours, with intermittent exercise and rest. Subjects will alternate 15 minutes of exercise on a cycle ergometer (intensity needed to achieve 20 L/min/m^2 BSA determined at baseline visit) with 15 minutes of rest.
9. Symptom questionnaire (immediately prior to exit from the chamber)
10. Immediately following exit from chamber, subjects will receive either 60 mg of prednisone or placebo per randomization schema
11. MCC (2 hours post-exposure)
12. Symptom questionnaire (6 hours post-WSP exposure)
13. EBC (4 hours post-WSP exposure)
14. Spirometry (4 hours post-WSP exposure)
15. Sputum Induction (4 hours post-WSP exposure)
16. Venipuncture for CBC with differential, serum cytokines, CRP (4 hours post-WSP exposure)

**4.6 Visits 4 (Period 1) and 8 (Period 2) (24 hours post-WSP exposure)**

1. Review any adverse events
2. Vital signs, oxygen saturation
3. Symptom questionnaire
4. Physical exam
5. EBC
6. Retention scan
7. Spirometry
8. Sputum Induction
9. Venipuncture for CBC with differential, serum cytokines, CRP

*Participants will be contacted by phone 3-7 days following Visit 4 to assess for any delayed adverse events. No phone call will be made after Visit 8 as participants will be returning for a study completion visit as below.*

*A 4 week washout is required between Period 1 and Period 2 for resolution of airway inflammation elicited following WSP exposure in Period 1.*

**4.7 Visit 5: Baseline (Period 2) (following a minimum 4 week washout)**

1. Review medical history and adverse events
2. Urine pregnancy test
3. Vital signs, oxygen saturation
4. Physical Exam
5. MCC
6. Spirometry
7. Sputum Induction
8. Venipuncture (safety labs only – CBC w/ diff)

**4.8 Visit 6: Retention Scan (Period 2) (24 hours after visit 5)**

1. MCC retention Scan (30 minutes)

**4.9 Visit 9: Study Completion [5-10 days following WSP exposure during Period 2 (Visit 7)]**

1. Review any adverse events
2. Vital signs, oxygen saturation
3. If the participant has any health symptoms or concerns, they will receive a physical examination and evaluation by a study physician.

**4.10 Unscheduled visits**

Any subject who has an unexpected adverse event (AE) as a result of the study treatment will have access to and contact information for a study physician. Subjects will be invited back to the lab for vital signs collection, physical exam, and spirometry as deemed necessary by the study physician. If the subject has any AE not associated with the study, he/she will not complete the study until the AE resolves such that it does not interfere with the study or with safety. If this causes a visit to be out of window, the subject can have an unscheduled visit at the discretion of the PI.

**4.11 Concomitant Medication documentation**

Concomitant medications are collected at the screening visit and throughout the study visits.

**4.12 Rescue medication administration**

As the study population consists of healthy volunteers, we do not anticipate subjects requiring any rescue medication administration. However, in the event that subjects experience bronchospasm with symptoms of cough, chest tightness, or wheezing associated with WSP exposure, the subject will be evaluated by a study physician. If necessary, rescue medication in the form of albuterol, a short-acting bronchodilator, will be readily available and administered per study physician recommendations. There is also a code cart immediately available with epinephrine autoinjectors. Oxygen is available for supplementation if required.

#### **4.13 Subject Withdrawal and Study Suspension Procedures**

Subjects may withdraw at any point in the study and will be asked to return to the lab for a final visit if they withdraw from the study prior to completion of all study procedures to monitor safety. Subjects may be withdrawn at any time for safety concerns.

Criteria for safety prior to initiation of wood smoke inhalation challenge: (Subjects not meeting these criteria the morning of challenge will not proceed with wood smoke inhalation challenge):

1. FEV1 of at least 80% of predicted and FEV1/FVC ratio of  $\geq 0.70$ .
2. Baseline oxygen saturation of at least 93%.
3. No history of physician-diagnosis asthma or frequent cough, wheezing, or shortness of breath consistent with a history of asthma.
4. No history of viral respiratory tract symptoms within 4 weeks of challenge.
5. No current symptoms of rhinorrhea, sneezing, nasal or ocular pruritus consistent with allergic rhinoconjunctivitis.

Criteria for safety of a given individual following WSP exposure and treatment which would suspend the individual from further participation in the study will include: (Subjects will be withdrawn for the following reasons):

1. Failure of return of FEV1 without treatment to within 90 % of baseline within 6 hours.
2. A symptom score greater than 45 (representing a ranking of “moderate” on each of 15 criteria, with a maximum score of 60, see appendix) without improvement to a score of 15 or less within 6 hours without therapy.
3. Specifically, a symptom score greater than “moderate” (3 on a scale of 0-4) for shortness of breath or cough at 24 hours post-challenge.
4. A reduction in oxygen saturation to <93% during the 4 hour observation period post-WSP exposure
5. Need for rescue albuterol therapy during the 4 hours observation period post-WSP exposure

Criteria for safety within the entire protocol (failure of which would result in suspension of further study until consultation with study sponsor, UNC IRB, and DSMB) will include the following: (Study will be suspended for the following reasons):

1. If 3 of the first 10 participants fail the individual safety criteria outlined above
2. Once 10 subjects have been enrolled, study suspension will occur if more than 25% of all participants fail the individual safety criteria outlined above
3. Occurrence of any study-related Serious Adverse Event (SAE)

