	
All measurements will be performed at baseline and again 4 hours post-WPS exposure, except for MCC which will be performed starting 2 hours after WSP exposure with measurements taken for a total of 120 minutes. Sputum induction will also be performed 24 hours post WSP challenge. The change in these measurements (postWSP – preWSP) will be compared for each interventional arm (prednisone vs placebo).

Safety Evaluations	
Vital signs, symptom questionnaire, spirometry

Statistical And Analytic Plan	
Our primary endpoint is the change in sputum %PMNs from baseline to 4 hours post-WSP exposure, comparing a single dose of prednisone to placebo. This analysis will rely on a linear mixed-effects model that accounts for the treatment effect and the period effect. Analysis of secondary endpoints (change in %PMNs 24 hours post WSP challenge, total mucin concentration, mucus composition, MCC, sputum and EBC inflammatory and oxidative stress markers, and systematic inflammatory markers, comparing a single dose of oral prednisone to matching placebo) will be performed similarly. The experiment-wide rate of Type I errors will be controlled at level <math>\alpha = 0.05</math>. Non-significant tests will be reported as being inconclusive.

DATA AND SAFETY MONITORING PLAN	
A study coordinator will enter data into REDCap, and then a second person will verify the data. Subjects will be monitored in real time for safety by study staff. A study physician will be immediately available during inhalation and treatment procedures and will determine the severity and relatedness of any adverse events (AEs). The PI will conduct ongoing assessment of safety with strict adherence to pre-specified study-suspension rules. All serious adverse events (SAEs) will be reported to UNC IRB and funding agency within 24 hours, and all AEs will be reported to UNC IRB and funding agency annually. A formal NC TracS Data Safety Monitoring Board (DSMB) charter meeting DOD approval will be established prior to commencing study. The DSMB will address issues regarding safety concerns, efficacy concerns, termination of the trial due to pre-specified stopping criteria, and ethical concerns. The DSMB will be furnished with relevant information by the Principal Investigator to make these decisions.

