## **5.2 Pharmacokinetic Evaluation: n/a**

## **5.3 Safety Evaluations**

Safety evaluations will be performed with the following measures with strict adherence to subject withdrawal and study suspension criteria (Section 4.10):

- a) Physical exam and vital signs: In addition to a limited physical exam of the eyes, ears, nose, throat, and respiratory and cardiovascular systems, we will also check vital signs (temperature, HR, BP, RR, and oxygen saturations) at each baseline visit (0 and 5), pre-WSP and 4 hours post-WSP exposure (visits 3 and 7), and 24-hours post-WSP (visits 4 and 8). Additional exams and vital signs will be performed at physician discretion if needed based on the participant's symptoms.
- b) Spirometry: Spirometry will also be performed at each baseline visit (0 and 5), pre-WSP and 4 hours post-WSP exposure (visits 3 and 7), and 24-hours post-WSP (visits 4 and 8). Healthy volunteers have been shown to tolerate WSP exposure well without any changes in lung function (21). However, if participants assign a score greater than 3 ("moderate") to symptoms attributable to bronchospasm (cough, wheezing, chest tightness, shortness of breath, or pain on deep inspiration) following WSP exposure, then they will be evaluated by the study physician to determine if additional spirometry and/or rescue treatment with albuterol is necessary. Additional spirometry will be performed at physician discretion.
- c) Symptom questionnaire (see Appendix): This will be performed pre-WSP, immediately before exiting WSP chamber, and 4 hours post-WSP exposure (visits 3 and 7), and 24-hours post-WSP (visits 4 and 8). Symptoms may be accessed at other time points during the study per physician discretion.
- d) Direct observation: Participants will remain under the direct observation of a study coordinator and study physician throughout each study visit and will be monitored for a minimum of 5 hours following each WSP exposure.
- e) Post-study visit safety plan: We do not anticipate any delayed adverse events. However, all participants will have access to and contact information for a study

physician during the duration of their participation. Per study physician recommendations, they will be re-evaluated with an unscheduled visit as detailed in Sections 3.1 and 4.10. Additionally, all subjects will be contacted via phone by a study coordinator 3-7 days after visit 4 to access for any delayed adverse events as noted in Section 4.6 above.

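### The only 24-hour withdrawal criterion omits wheezing and chest tightness, so a severe score on either alone neither mandates withdrawal nor counts towards study suspension

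*Combined protocol and SAP*

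**What the plan says.** Section 4.13 gives five criteria for withdrawing a subject after wood smoke exposure:

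- Criterion 1 (FEV1 recovery) and criterion 2 (total symptom score) are tied to 6 hours.
- Criterion 4 (oxygen saturation) and criterion 5 (rescue albuterol) are tied to the 4-hour observation period.
- Criterion 3 is the only one set at 24 hours. It requires a score above moderate, given as "3 on a scale of 0-4) for shortness of breath or cough at 24 hours post-challenge".

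The same section then sets three rules for suspending the study. The first applies "If 3 of the first 10 participants fail the individual safety criteria outlined above". The second applies once 10 subjects are enrolled, if more than 25% of participants fail those same criteria. The third is any study-related serious adverse event. The Synopsis promises "strict adherence to pre-specified study-suspension rules", and section 5.3 introduces the safety measures "with strict adherence to subject withdrawal and study suspension criteria".

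Two other places describe what bronchospasm looks like in this trial. Section 4.12 refers to "bronchospasm with symptoms of cough, chest tightness, or wheezing associated with WSP exposure". Section 5.3(b) sends a subject to the study physician for a score above 3 on "symptoms attributable to bronchospasm (cough, wheezing, chest tightness, shortness of breath, or pain on deep inspiration) following WSP exposure".

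Section 4.13 also allows discretion: "Subjects may be withdrawn at any time for safety concerns".

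**The concern.** Criterion 3 makes a severe cough at 24 hours a reason for withdrawal but not a severe wheeze or severe chest tightness. The protocol elsewhere groups these three symptoms together, and the documents give no reason for treating them differently at 24 hours.

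What is at stake is mainly the count. Both numeric suspension rules count failures of the listed criteria, not withdrawals in general and not physician evaluations. A severe 24-hour reaction outside the list is therefore not counted, even if the physician acts on it.

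Section 9 extends the effect. The first limb of its adverse event definition is failure of these same safety criteria. An isolated 24-hour score of 4 on an omitted symptom is not an adverse event under that limb. It becomes one under the second limb only if the symptoms lead the volunteer to seek medical attention within 96 hours of a study visit. The DSMB's review of adverse events may therefore not pick it up either.

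After Period 1 the gap affects both mandatory withdrawal before a second exposure and the count. After Period 2 it affects mainly the count.

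**Working it through.** **Step 1: reproduce the plan's symptom-score figures.** The Appendix questionnaire has 15 items scored 0 to 4. Moderate on every item gives 15 × 3 = 45 and the maximum is 15 × 4 = 60, both as section 4.13 states. A score above 3 on a single item means a score of 4, labelled severe.

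**Step 2: see whether another criterion catches the subject.** Take a subject with 4 on both wheezing and chest tightness at 24 hours, and 3 on both cough and shortness of breath.

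| Criterion (4.13) | Time | Caught by the 24-hour scores? |
|---|---|---|
| 1. FEV1 recovery | 6 h | No, unless already failed at 6 h |
| 2. Total above 45, not down to 15 or less | 6 h | No: outside the window, and see below |
| 3. Shortness of breath or cough above 3 | 24 h | No: both are 3 or below |
| 4. Saturation below 93% | 4 h period | No, unless already failed |
| 5. Rescue albuterol | 4 h period | No: albuterol at 24 h is outside the window |

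Criterion 2 would rarely help even if it were read as applying at 24 hours. The two omitted symptoms contribute 2 × 4 = 8, and cough and shortness of breath add 2 × 3 = 6, giving 14. Reaching 46 would take another 32 points from the remaining 11 items, an average of about 2.9 each.

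The gap is therefore a subject who passed criteria 1, 2, 4 and 5 and scores 4 at 24 hours on wheezing or chest tightness, with cough and shortness of breath at 3 or below.

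**Step 3: find the suspension thresholds.** Planned enrolment is 14 (section 3.3). Failures needed to exceed 25%:

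| Enrolled | 25% of enrolled | Failures needed |
|---|---|---|
| 10 | 2.5 | 3 |
| 11 | 2.75 | 3 |
| 12 | 3.0 | 4 |
| 13 | 3.25 | 4 |
| 14 | 3.5 | 4 |

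**Step 4: effect of one uncounted subject when the count is one short.**

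- At 10 enrolled: 2/10 = 20%, no suspension; if counted, 3/10 = 30%, suspension.
- At 14 enrolled: 3/14 = 21.4%, no suspension; if counted, 4/14 = 28.6%, suspension.

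**Step 5: compare the symptom lists.**

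| Symptom | Criterion 3 (4.13) | Bronchospasm (4.12) | Evaluation, score above 3 (5.3(b)) |
|---|---|---|---|
| Cough | yes | yes | yes |
| Shortness of breath | yes | no | yes |
| Wheezing | no | yes | yes |
| Chest tightness | no | yes | yes |
| Pain on deep inspiration | no | no | yes |

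Wheezing and chest tightness appear in both other lists; inspiratory pain appears only in 5.3(b). The pre-challenge check in 4.13 also names wheezing, in "frequent cough, wheezing, or shortness of breath consistent with a history of asthma", but it concerns asthma history rather than response to exposure and carries less weight.

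**The case against.** The best answer is that this is a design choice. Section 5.3(b) decides whom a physician looks at, and criterion 3 decides who is removed. A broad evaluation list beside a narrower removal list is ordinary, and strict adherence is satisfied by following the rules as written. This stands to the extent that the plan contains no contradiction. It does not explain why severe cough is on the removal list and severe wheeze is not.

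A second answer is that real bronchospasm lasting to 24 hours could already have failed the FEV1, saturation or albuterol criterion and been counted. That is right, and it makes the gap narrow.

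A third is that the subject is well looked after. A reader might infer that severe wheeze at 24 hours goes unattended; the documents do not support that. Visits 4 and 8 (section 4.6) include adverse event review, vital signs, saturation, physical examination and spirometry. Section 5.3(b) sends the subject to a physician, and withdrawal at discretion is available. Before the second exposure there is also a phone call, the Visit 5 review and the morning-of-challenge checks. These protect the individual, but none of them adds to the two numeric counts.

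The introduction to the withdrawal criteria could be read as open-ended. Its parenthetical, however, points to the reasons that follow, and a numeric rule needs defined events to count.

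A reader might also infer that all five symptoms in 5.3(b) belong in criterion 3. The documents do not go that far: inspiratory pain is only an evaluation trigger, and making it a mandatory removal trigger is a matter of judgement.

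**Conclusion.** The point holds as a narrow gap of the lowest severity. Criterion 3 is the only listed individual criterion at 24 hours, and it omits two symptoms that the protocol itself associates with bronchospasm. A subject in the gap adds 0 to both numeric suspension counts and can change the outcome only when the count is exactly one short.

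This assumes that the listed criteria are the events to be counted and that the subject passed criteria 1, 2, 4 and 5.

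A reader might infer that the suspension rules are likely to fail. The documents do not support this. They give no rate for an isolated 24-hour score of 4 on wheezing or chest tightness, and section 9 reports neither symptom in an earlier study of healthy volunteers exposed to wood smoke. Such events are expected to be rare, and no probability is claimed. A study-related serious adverse event would suspend the study in any case.

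**What to change.** Reword criterion 3 in section 4.13 so that it applies to a score above moderate (above 3 on the 0-4 scale) at 24 hours after challenge for any of shortness of breath, cough, wheezing or chest tightness. Inspiratory pain may be added at the investigator's judgement. State that, for counting failures, the new wording also applies to the 24-hour questionnaires already collected. Section 6.5 reports 7 subjects enrolled and 6 completed before the pandemic pause, and these fall within the first 10.

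The change is one line. The questionnaire is already completed at Visits 4 and 8 and contains both items, so no new visit, form or test is needed.

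The cost is a small added chance of an earlier suspension review or of losing a Period 2 dataset. Section 6.5 plans 14 subjects for 12 complete datasets, a margin of 14 − 12 = 2. Inadequate samples at 5-10% of 14 would use 0.7 to 1.4 of that, leaving 0.6 to 1.3, so one extra removal after Period 1 could use what remains. A removal triggered at Visit 8 would not cost the 4-hour primary comparison, because those data are already collected.

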#### **4.14 Screen failure procedures**

For subjects who do not meet enrollment criteria, all study related activity will stop once it is determined that the subject does not meet criteria.

### **5 STUDY EVALUATIONS AND MEASUREMENTS**

- **List variables that will be abstracted from medical charts:** none
- **Describe baseline evaluation**

As listed above for baseline visit and training visit of period 1 (Section 4.2), vital signs, including HR, RR, temperature and BP will be collected after a thorough review of the medical history. Oxygen saturation levels will also be noted followed by a brief physical examination, including but not limited to the cervical lymph nodes, eyes, ears, nose, throat, cardiovascular and respiratory systems. Laboratory evaluations will include urine pregnancy test and venipuncture (see below for details). In addition, baseline spirometry, MCC, EBC, and sputum induction will be performed as detailed below. Subjects will also undergo training on the cycle ergometer to reach an exercise level producing a minute ventilation of 20 L/min/m^2 BSA in preparation for the WSP exposure during Visits 3 (period 1) and 7 (period 2). Baseline visit for period 2 (Section 4.5 above) will include all of the measurements obtained for baseline visit and training visit of period 1, but subjects will not require additional training on the cycle ergometer.

- **Describe how measurements will be taken.**

- a) Woodsmoke particle chamber exposure: We will employ the exposure protocol as described by Ghio and colleagues (21). We will heat red oak wood on an electric heating element (Brinkmann, Dallas, Texas, USA) in a Quadrafire 3100 woodstove (Colville, Washington, USA) at 800°F to generate wood smoke. The smoke will be extracted from the chimney and injected into the chamber air stream, and WSP concentration will be controlled using a tapered element oscillating microbalance (TEOM; Thermo Fisher Scientific, Franklin, Massachusetts, USA) to measure the chamber concentration. A Model DR-4000 DataRAM (Thermo Fisher Scientific) will also be used to measure the concentration. The particle number concentration will be measured with a Model 3775(TSI, Shoreview, Minnesota, USA) and the number and size distribution will be measured with a Model 3936L75 SMPS (TSI). The particle concentration will be verified by weighing filters obtained using a versatile air pollution sampler (VAPS; URG, Chapel Hill, North Carolina, USA). The chamber temperature and humidity will be controlled to approximately 22°C and 40%, respectively. The concentrations of WSP we will use for this study will not exceed 500 µg/m^3, with mild exercise to increase minute ventilation (20 L/min/m^2 BSA) for 15 minute periods, alternating with 15 minute rest periods across an overall 2 hour total exposure period. Subjects will be trained during Visit 0 on the cycle ergometer to reach this minute ventilation. A 12 lead-EKG will be performed prior to training for safety purposes, and subjects will be monitored with a standard 3 lead EKG during exercise.
- b) Sputum Induction: Sputum samples will be collected using a specific sputum induction protocol in which FEV1 and FVC will be measured to determine the baseline FEV1 and FVC values. The FEV1 values that match a 10% and 20% fall from baseline will be calculated. An ultrasonic nebulizer will be filled with 15 mL of 3% hypertonic saline (inhalation grade for respiratory use only) to begin the test. The nebulizer will be set to the maximum output setting and turned on. The subject will be instructed to breathe normally (i.e. tidal breaths) through the nebulizer mouthpiece for 7 minutes. The saline will be nebulized through the mouthpiece in a jet stream and inhaled. The nose will not be occluded for this procedure. Prior to expectoration, subjects will blow their nose, rinse their mouth with water, and clear their throat to avoid the inclusion of non-airway fluid samples. The subject will also be encouraged to come off the mouthpiece at any time to cough if a sputum sample from the lower airways (i.e. not from the back of the throat) is ready for expectoration. The sample will

be coughed into a sterile specimen jar and capped. Following repeat measurement of FEV1 after the first inhalation period, the concentration of saline will be increased from 3% to 4%, provided the FEV1 falls by <10% from the baseline value. The same procedure will be followed for the final inhalation period using 5% hypertonic saline. The nebulization will be stopped at that point, or earlier, if a sputum sample of good quality is obtained (i.e. visible sputum plugs). The 4% and 5% saline solutions will be mixed for each induction by study staff just prior to induction and a volume of 15-20 mL will be used on each occasion. Participants will not be pre-treated with Albuterol as is our standard procedure with healthy volunteers. Albuterol will be available if needed. Sputum sample will be used to evaluate for mucus-based parameters, such as total mucin concentration, % solid content, and MUC5AC/MUC5B.

- c) Spirometry: Spirometry will be performed according to American Thoracic Society (ATS) guidelines. Subjects will inhale as deeply as possible then exhale as rapidly and completely as possible into the spirometer. Measurements obtained from each maneuver include the FVC, the FEV1, the maximal mid-expiratory flow rate (FEF25-75) and the peak flow. The largest FVC and FEV1, from at least 3 acceptable trials will be selected for analysis and subject must meet the appropriate inclusion/exclusion criteria based on comparison of the subject's measurements to the predicted value for an individual of his/her gender, age, race and height with NHANES III as the predicted set.
- d) Exhaled breath condensate: EBC will be collected at individual study sites via established protocols (22) using the commercially available RTube (Respiratory Research, Inc., Charlottesville, VA)—a handheld, self-contained, single-use device. The device consists of a mouthpiece connected to a one-way valve that directs exhaled breath through a condenser tube cooled by a cooling sleeve. Gaseous phase liquid and aerosols in exhaled breath condense into liquid form on the inside surface of the chilled condenser tube and can be extracted using a plunger device supplied by the manufacturer. The specific collection protocol would include chilling the aluminum cooling sleeve to -20° C, then placing this cooling sleeve with insulated cover over the RTube device immediately before collection. Once the cooling sleeve is in place, the subject breathes tidally through the mouthpiece for 15 minutes. EBC samples are stored at -80° C pending analysis.
- e) Mucociliary clearance: Prior to each MCC study, a transmission Cobalt57 (Co57) scan will be performed to define the lung boundaries, to assign regions of interest, and to normalize these regions for lung volume differences. A rectangular phantom containing the radioisotope Co57 (<25 microcurie (mCi)) will be placed in front (5cm) of the subject sitting with his/her back to the gamma camera for 30 seconds. Prior to the transmission scan before each MCC assessment, we will place 2 spot markers of Americium241 (0.9 mCi each, gamma 66 kilo electron volts) on the upper and lower back of each subject during scanning (both Tc99m-SC deposition/retention and Co57 transmission). With dual isotope imaging, these spot markers will allow alignment of images for more accurate determination of regional deposition/retention. These very low radiation sources have been obtained from commercially available home smoke alarms. The placement of these markers will be determined to be

outside the lung field during the transmission scan. Their location will be marked in semi-permanent ink for later placement during Tc99m deposition/retention scans. The shielded side of this source will be placed/taped onto the subject's skin.

Radiolabeled Tc99m-SD will be delivered using a modified Pari-LC Star nebulizer (MMAD 9.5 um). This is a closed delivery system that produces 80 ml/sec air flow, and therefore limits the inspiratory flow rate to this value. While seated in front of a gamma camera subjects will perform single inhalations lasting ~10 seconds each from the delivery system, and will exhale at 500 ml/sec (using feedback from a flow meter in the breathing circuit). Approximately 5 of these inhalation maneuvers will be required to deposit an adequate isotope dose to the lung. Subjects will be allowed to breathe normally (off the nebulizer) in between each inspiratory maneuver. Each volunteer will practice these maneuvers prior to the actual radioaerosol inhalation to guarantee his/her proficiency. The activity of Tc99m-SC loaded in the nebulizer will be adjusted to provide an estimated 40 mCi deposited in the lung for each MCC scan. A single crystal detector will be placed at the subject's back during inhalation to monitor dose to the lung. Total inhalation time should be less than 5 minutes in all cases. Immediately following isotope inhalation, the subject will gargle and drink water to clear activity that deposited in the mouth into the stomach. The subject will then (within a minute of final inhalation maneuver) be seated in front of a large-field-of-view gamma camera to begin acquiring particle retention images.

For each MCC measurement, the gamma image capture will capture continuously for the first 34 minutes after which 2 consecutive 2-minute images will be obtained at the start of every 10-minute period until 2 hours have passed. The subject will also return the day following each MCC measurement to sit in front of the gamma camera for 30 minutes to obtain images of the lungs to visualize retention of Tc99m-SC particles. No additional Tc99m-SC will be administered at this visit.

- **Describe rating scales, tests, psychological tools, laboratory evaluations, etc.**
  - a) Urine pregnancy test (UPT): A UPT will be obtained on all females who are not s/p hysterectomy with oophorectomy at visits 0, 1, 3, 5, and 7. If positive, these women will be excluded from the study. UPTs are valid for 7 days.
  - b) Venipuncture: Blood will be drawn to evaluate a CBC with differential, CRP, and inflammatory cytokine profile pre- and post-WSP exposure at Visits 3 and 7. At the time of each venipuncture, up to 50 cc will be drawn, and the total for the study will be no more than 200 cc.
  - c) Symptom questionnaire: To access for safety throughout the study, symptom questionnaires will be performed at pre-WSP exposure (visits 3 and 7), immediately post-WSP exposure, 6 hours post-WSP exposure, and 24 hours post-WSP exposure (visit 4 and 8). The questionnaire consists of 15 symptoms, requiring a rating from 0-4 with a minimum score of 0 and maximum score of 60. See Appendix for symptom questionnaire.

